**SECTION I: RESEARCH PLAN**

**1. Statement of Purpose:** State the scientific aim(s) of the study, or the hypotheses to be tested.

Dysregulated glutamate signaling is a hallmark of chronic alcohol abuse. Acute alcohol at clinically relevant doses stimulates glutamate release, while chronic alcohol leads to enhanced glutamatergic activity. When chronic alcohol is removed, as in withdrawal, a 'hyperglutamatergic state' results, characterized by excessive excitatory signaling and heightened extracellular glutamate levels. These alterations to glutamate signaling may be particularly relevant for alcohol craving and relapse propensity. While these dynamics are well characterized in rodent models, limited techniques have stalled translation of these findings to human research. Characterization of dynamic glutamate release in people would dramatically advance our understanding of aberrant glutamate function in alcohol use disorder. **This underscores the need for innovative approaches that measure alcohol-induced glutamate release in humans.**

Positron emission tomography (PET) imaging with radiotracers specific to the metabotropic glutamate receptor 5 (mGlu5), [F]FPEB and [C]ABP688, provide an established technique to measure glutamate release. Ketamine, which elicits glutamate release, robustly reduces radiotracer distribution volumes ( $V_T$ ) in human brain. **We propose to leverage this imaging technique to measure alcohol-induced glutamate release in people.** However, these radiotracers exhibit subtle differences in the mechanism by which glutamate reduces mGluR5 availability. Therefore, in **Aims 1 and 2** we will evaluate both radiotracers and compare their effects to determine the optimal experimental approach. Each Aim will recruit 10 moderate drinkers who do NOT meet DSM-5 criterion for alcohol use disorder. We will strive to recruit the same subjects to participate in both Aims 1 and 2 for a direct comparison between approaches. For each aim, two mGlu5 PET measurements with arterial blood sampling will be acquired. Scanning will begin immediately following alcohol administration that will achieve 60 mg/dL for at no more than one hour, timed to capture the window of peak glutamate levels. This alcohol dose is similar to doses eliciting glutamate release in rodents and dopamine release in people. Subjective alcohol effects will be evaluated with the Biphasic Alcohol Effects Scale at baseline and every 30 min after alcohol for 90 min. The study will administer alcohol as an oral alcohol challenge first, however if sufficient

glutamate release is not achieved orally, then they study will switch to IV alcohol as the challenge in subsequent testing. The collected data will be used to accomplish the following specific aims:

**In Aim 1 we will determine the sensitivity of the PET radioligand [F]FPEB to the glutamate response from a fixed-dose alcohol session.** [F]FPEB  $V_T$ , an index of the number of mGlu5 available for radioligand binding, will be estimated throughout the brain. We hypothesize that alcohol will significantly reduce [F]FPEB  $V_T$  in the prefrontal cortex and striatum compared to baseline, consistent with glutamate release. The prefrontal cortex and striatum are brain regions with reported alcohol-induced glutamate release in preclinical models.

**In Aim 2 we will determine the sensitivity of the PET radioligand [C]ABP688 to the glutamate response from a fixed-dose alcohol session.** [C]ABP688  $V_T$ , an index of the number of mGlu5 available for radioligand binding, will be estimated throughout the brain. We hypothesize that alcohol will significantly reduce [C]ABP688  $V_T$  in the prefrontal cortex and striatum compared to baseline, consistent with glutamate release. The prefrontal cortex and striatum are brain regions with reported alcohol-induced glutamate release in preclinical models.

The route of alcohol administration has important effects on brain neurochemistry. While oral alcohol provides a more naturalistic route of administration, the effects of first pass metabolism and gut absorption result in slower acute brain effects, which neuroimaging studies are typically less sensitive to. Therefore, the research plan will first evaluate the glutamate response to acute oral alcohol. However, given the diminished sensitivity of neuroimaging to this route of administration, should no effects of oral alcohol on brain neurochemistry be detected, we then plan to test for sensitivity to i.v. alcohol to leverage the more potent acute effects. This question of route of administration is a critical question in the experimental paradigm optimization, and will be addressed in subaims 1A, 1B, and 2A, 2B, respectively, before continuing to Aim 3.

Based on the results of the first aims, we will identify an optimal experimental paradigm. Using this approach, we next will recruit 30 moderate drinkers and 30 people who meet DSM-5 criteria for alcohol use disorder. Subjects will self-report recent and lifetime drinking patterns. Alcohol-induced glutamate release will be measured with ONE of the experimental approaches identified above to accomplish the following aim:

**In Aim 3 we will compare the alcohol-induced glutamate release in moderate drinkers and individuals with alcohol use disorder.** Chronic alcohol exposure is associated with heightened extracellular glutamate levels. This may contribute to tolerance by diminishing alcohol-induced glutamate release. We hypothesize that more people with AUD will have predict smaller changes in radioligand  $V_T$  ( $\Delta V_T$ ) after alcohol compared to moderate drinkers. Such a relationship would provide evidence of dynamic neuroadaptations of glutamatergic signaling relevant to the development and treatment of alcohol use disorder.

As an exploratory aim, we will investigate relationships between subjective effects and the amount of alcohol-induced glutamate release. Diminished subjective effects may also be associated lower amounts of glutamate release ( $\Delta V_T$ ), consistent with previously observed preclinical neuroadaptations. Successful completion of these aims will provide valuable data that will illuminate the role of glutamate in alcohol use disorder and subsequent withdrawal. The findings will inform and evaluate treatment approaches targeting the glutamate system for alcohol use disorder.

2. **Probable Duration of Project:** State the expected duration of the project, including all follow-up and data analysis activities.  
10 Years
3. **Background:** Describe the background information that led to the plan for this project. Provide references to support the expectation of obtaining useful scientific data.

### Glutamate Function and Neural Reorganization During Alcohol Withdrawal

Alcohol dependence affects over 10% of the population, accruing great cost to individuals and society. Chronic alcohol exposure distorts brain structure and function, inducing gray matter atrophy, altering function of neurotransmitter systems, and modifying neural organization as evaluated by functional magnetic resonance imaging (fMRI) connectivity measures. During extended withdrawal, the alcohol dependent brain again undergoes dynamic changes, which have vital implications for treatment outcome. Since up to 80% of treated abstinence cases result in later problematic drinking, we must improve our understanding of how changing brain architecture during withdrawal influences relapse-associated behaviors. These advancements can inform the development of therapies targeting the underlying neural basis of relapse identified by neuroimaging biomarkers rather than treating behavioral or cognitive symptoms themselves.

Glutamate, the major excitatory neurotransmitter, heavily influences cerebral neuroplasticity and has complex interactions with alcohol dependence. Interventions targeting the glutamate system may impede relapse while hastening neural reorganization. Acute alcohol directly acts at *N*-methyl-D-aspartate receptors (NMDAR), limiting cortical excitability and indirectly disinhibiting glutamate release. Chronic alcohol exposure upregulates NMDAR subunits. Subsequent withdrawal induces a “hyperglutamatergic” state, characterized by excessive excitatory signaling and extracellular glutamate levels. These aggregate changes to glutamate signaling increase relapse propensity. However, no methods currently exist that directly measure glutamate release in people. This research project will dramatically advance our ability to develop and evaluate therapies for alcohol use disorder.

### PET Imaging of mGlu5 Receptors

Glutamate neurotransmission is regulated by ionotropic and the G-protein coupled metabotropic glutamate receptors (mGluR), which are divided into 3 groups: group I (mGluR1 and 5), group II (mGluR2 and 3) and group III (mGluR4, 6, 7, 8). To date, the most successful PET radioligands used to image the glutamate system target the metabotropic glutamate 5 (mGlu5) receptor. MGlur5 receptors are located postsynaptically and on glia, and have highest density in the hippocampus, intermediate in the caudate/putamen, cerebral cortex, deep cerebellar nuclei, and thalamus, and lowest in the cerebellum.

The two PET radioligands most prominently used to image mGlu5 in humans are [F]FPEB and [C]ABP688. Both radioligands bind with high specificity and affinity to a negative allosteric site on mGlu5. Both radioligands are synthesized in the Radiochemistry Lab at the Yale PET Center. Production of [F]FPEB and [C]ABP688 for use in research protocols involving human subjects are both separately approved by the Yale University Radioactive Drug Research Committee (YU RDRC). Recent work conducted by our colleague, [name], and others have demonstrated that both ligands are sensitive to ketamine, which is thought to trigger glutamate release. These findings motivate a similar approach to measure glutamate release triggered by alcohol exposure.

4. **Research Plan:** Summarize the study design and research procedures using non-technical language that can be readily understood by someone outside the discipline. **Be sure to distinguish between standard of care vs. research procedures when applicable, and include any flowcharts of visits specifying their individual times and lengths.** Describe the setting in which the research will take place.

#### **4.1 Overall Research Design:**

This research plan proposes experiments that are critical to advance our understanding of glutamatergic signaling in alcohol use disorders. We will recruit moderate drinkers and Alcohol Use Disorder subjects between the ages of 21 to 55 years to participate in the recruitment, evaluation, and imaging. Moderate drinkers are defined as people who report consuming alcohol on at least one occasion in the past three months that would result in an estimated blood alcohol level greater than 80 mg/dl but not meet DSM-5 criteria for AUD. This is operationally defined as more than 3 standard drinks in a single occasion for women and 4 standard drinks in a single occasion for men. All participating subjects will be seen for an initial intake, including a full physical exam and medical coding. Thereafter, they will have an anatomical MRI scan, followed by a series of [C]ABP688 and/or [F]FPEB PET scans with alcohol challenge as described in the below aims:

**Aim 1** will evaluate the sensitivity of the mGlu5 radioligand [F]FPEB to alcohol release in the same subjects (moderate drinkers,  $n=10$ ). Subjects will participate in up to two [F]FPEB scans with alcohol challenge that measure mGlu5 availability under the following conditions: baseline and 60 mg/dL alcohol administration. This will be conducted with the following sub-aims:

**Aim 1a** will administer the alcohol (targeting 60 mg/dL) as an oral challenge. This will be done in at least the first 5 subjects. At this point, the percent change in mGlu5 receptor availability (i.e., [F]FPEB  $V_T$ ) will be evaluated. If this remains within test-retest estimates of this radiotracer (9-12%) {Park, 2015 #219} in subjects achieving the targeted alcohol dose, then we may proceed to Aim 1b:

**Aim 1b** will administer the alcohol (targeting 60 mg/dL) as an i.v. challenge.

**Aim 2** will evaluate the sensitivity of the mGlu5 radioligand [C]ABP688 to alcohol release in the same subjects (moderate drinkers,  $n=10$ ). Subjects will participate in up to two [C]ABP688 scans with alcohol challenge that measure mGlu5 availability under the following conditions: baseline and 60 mg/dL alcohol administration. This will be conducted with the following sub-aims:

**Aim 2a** will administer the alcohol (targeting 60 mg/dL) as an oral challenge. This will be done in at least the first 5 subjects. At this point, the percent change in mGlu5 receptor availability (i.e., [C]ABP688  $V_T$ ) will be evaluated. If this remain within test-retest estimates of this radiotracer (<12%) in subjects achieving the targeted alcohol dose, then we may proceed to Aim 2b:

**Aim 2b** will administer the alcohol (targeting 60 mg/dL) as an i.v. challenge.

We will strive to recruit the same subjects from Aim 1 for Aim 2, in order to directly compare the two experimental approaches in the same people.

The results of these two aims will inform the selection of an optimal experimental design.

**Aim 3** will compare the alcohol-induced glutamate release in moderate drinkers ( $n=30$ , including subjects from the chosen tracer from Aim 1 or 2) and individuals with alcohol use disorder ( $n=30$ ). Subjects will participate in up to two mGlu5 scans under the following conditions: baseline and 60 mg/dl alcohol administration.

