#### Breakdown of Aims 1-3

- Aim 1: 10 moderate drinkers
- Aim 2: 10 moderate drinkers

- Aim 3: 30 moderate drinkers (minus drinkers from chosen tracer in Aim 1 or 2), and 30 AUD

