##### **PET Scans**

PET experiments will be conducted at the Yale University PET Center. Subjects may have up to three [C]ABP688 PET scans, and/or up to three [F]FPEB PET scans for a maximum total of six scans (including possible rescheduled scans, 1 per tracer). Subjects will also be asked to refrain from drinking caffeinated beverages on imaging days, and from drinking alcoholic beverages 48 hours prior to imaging days.

Upon arrival at the PET center, subjects will complete questionnaires on urges, withdrawal symptoms, and mood. Plasma will be drawn before scans to measure drug levels in the blood. Urine drug tests will be performed before all PET scans. To ensure overnight abstinence for individuals with alcohol use disorder, subjects will be invited to stay inpatient at the CNRU the night before their PET scans unless there are scheduling conflicts with the subject. Confirmation of alcohol abstinence over the previous 48 hours will be made via self-report and BAC measures, and session will be rescheduled if positive.

*For all women, a urine pregnancy test will be performed at the beginning of the imaging day, prior to radiotracer injection, at the Yale University PET Center.*

For all aims, up to three total [F]FPEB PET scans may be acquired per subject. Imaging data will be acquired using bolus or bolus plus constant infusion of  $\leq 20$  mCi [F]FPEB. After baseline mGlu5 availability is measured, subjects will participate in i.v. alcohol infusion (targeting 60 mg/dL). This dose was selected to achieve mild to moderate levels of intoxication, consistent with the aims of the proposal. [F]FPEB PET scanning will begin as soon as possible (i.e., not more than 30 min after the subject completes the alcohol challenge) to capture the peak glutamate response. This timing is consistent with previous reports studying dopamine release in response to alcohol challenge. Blood samples will be collected throughout all [F]FPEB PET scans and during the alcohol administration.

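### After a switch from oral to i.v. alcohol, the tracer-only carry-over rule would place 5 to 9 oral-challenged subjects among the 30 Aim 3 controls and none in the AUD group

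*Combined protocol and SAP*

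**What the plan says.** All references are to the combined protocol and SAP.

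- **Carry-over rule.** Section 4.1, Aim 3, sets 30 moderate drinkers, "including subjects from the chosen tracer from Aim 1 or 2", against 30 people with AUD. The Breakdown of Aims 1-3 restates this as "30 moderate drinkers (minus drinkers from chosen tracer in Aim 1 or 2), and 30 AUD". Both sentences refer to tracer and neither mentions route.
- **Oral first.** Aims 1a and 2a give the oral challenge: "This will be done in at least the first 5 subjects". If the change in V_T stays within test-retest limits (9-12% for FPEB, below 12% for ABP688), the study may move to i.v. under Aims 1b and 2b. Each tracer has 10 subjects in total. The Statement of Purpose applies the switch to later testing only.
- **Importance of route.** The Statement of Purpose says "The route of alcohol administration has important effects on brain neurochemistry" and that this question "will be addressed in subaims 1A, 1B, and 2A, 2B, respectively, before continuing to Aim 3". It continues "Using this approach, we next will recruit 30 moderate drinkers and 30 people who meet DSM-5 criteria for alcohol use disorder" and "Alcohol-induced glutamate release will be measured with ONE of the experimental approaches identified above to accomplish the following aim".
- **Analysis.** Item 13 (Statistical Considerations), Aim 3, specifies a mixed model for ΔV_T with group, region and their interaction. It has no route term.
- **Headcount.** Item 6 (Subject Population) allows up to 70 people: 40 moderate drinkers and 30 with AUD.

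**The concern.** The plan treats route as important enough to settle before Aim 3, yet its rule for filling the control group ignores route. AUD subjects are recruited only after the approach is fixed, so they would all have the final route. Some controls would not.

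Two distortions follow, and both fall on the control group alone:

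1. **Confounding.** If oral alcohol produces a smaller fall in V_T than i.v., the oral controls pull the control mean towards zero and shrink the group difference that Aim 3 is meant to detect.
2. **Selection.** The switch is triggered by a small change in the first oral subjects. Carrying forward subjects whose low values caused the switch lowers the control mean even if the two routes have the same true effect.

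The direction is against the hypothesis of a smaller response in AUD. The main risk is a missed difference. If there is no true difference, the risk is a spurious result in the opposite direction.

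**Working it through.** **Headcount.** Aim 1 (10) + Aim 2 (10) + new Aim 3 controls (30 − 10 = 20) = 40 moderate drinkers. Adding 30 AUD gives 70, the stated total. If Aims 1 and 2 share no one, 40 is reached by counting all ten carried-over subjects whatever their route.

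**Oral controls after a switch.** Let k be the number of oral subjects among the ten on the chosen tracer. The minimum is k = 5. A switch within the ten needs at least one i.v. subject, so k is at most 9; k = 10 is a limiting case. The AUD count is 0 of 30.

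**Shift in the control mean** = (k/30) × (i.v. effect − oral effect): 5/30 = 16.7%, 9/30 = 30.0%, 10/30 = 33.3% of the oral–i.v. difference.

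**Rescanning.** No i.v. rescan of oral subjects is described. Each aim lists one baseline and one alcohol scan. The PET Scans section allows scans "for a maximum total of six scans (including possible rescheduled scans, 1 per tracer", and item 10 (radiation risks) ties an additional injection to scan failure.

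**Power illustration.** The documents give no effect sizes and no SD of change, so these inputs are assumptions: i.v. fall 15%, AUD fall 5%, SD of percentage change 12%, oral fall 0 to 15%. The method is a two-sample t-test simulation on one average region, 200,000 runs per cell, with all of the first five assumed to reach the target dose. The first five oral values are drawn conditional on their mean fall being below T (T = 9 or 12). Any further oral values are unconditional, and the other 30 − k controls are i.v.

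With one route throughout (30 v 30), power is 88.8% and the true difference is 10 points. With mixed routes, power in % (T = 9 / T = 12) is:

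| Oral fall | k = 5 | k = 9 | k = 10 |
|---|---|---|---|
| 0% | 61.2 / 62.1 | 34.2 / 35.2 | 28.4 / 28.9 |
| 5% | 69.8 / 71.9 | 52.8 / 55.2 | 48.3 / 50.8 |
| 10% | 75.1 / 78.5 | 67.5 / 71.4 | 65.5 / 69.5 |
| 15% (equal to i.v.) | 77.5 / 81.6 | 77.6 / 81.8 | 77.7 / 81.7 |

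The last row is selection alone: the realised mean of the first five is 6.3 / 8.6 instead of 15.

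**Expected group difference.** For oral falls of 0, 5 and 10%, it is 7.4–7.5, 8.0–8.2 and 8.3–8.7 points with k = 5, and 5.4–5.5, 6.7–6.8 and 7.7–8.0 with k = 9. Example (k = 5, oral fall 0, T = 9, first-five mean −0.5): (5 × (−0.5) + 25 × 15)/30 − 5 = 7.4.

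**Chance of a switch** = Φ((T − oral fall)/(12/√5)): 95–99%, 77–90%, 43–65% and 13–29% for oral falls of 0, 5, 10 and 15%.

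**Type I error** (AUD fall also 15%, two-sided, T = 9 / T = 12), for oral falls of 0, 5 and 10%:
- k = 5: 10.7 / 10.4, 8.4 / 8.0 and 7.1 / 6.3%.
- k = 9: 25.1 / 24.7, 16.1 / 15.1 and 10.0 / 8.8%.

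At most 0.65 percentage points of this lies in the hypothesised direction.

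**Route-matched controls only.** Power is 85.6% (25 v 30), 81.9% (21 v 30) and 80.8% (20 v 30), with the 10-point difference unbiased. The standard error ratio √(1/n + 1/30)/√(2/30) is 1.049, 1.102 and 1.118.

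**Sensitivity to SD** (9 / 15):
- One route: 98.9 / 71.6%.
- k = 5, oral fall 0, T = 9: 84.5 / 42.8%; route-matched 25 v 30: 98.1 / 67.5%.
- k = 9, oral fall 0, T = 9: 53.1 / 23.2%; route-matched 21 v 30: 96.9 / 63.2%.

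For k = 5 and 9, oral falls of 0–10% and SD 9–15, dropping the oral controls gives more power than keeping them in every cell.

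**The case against.** The strongest reply is that the plan already states its intent. The Statement of Purpose settles route first and commits Aim 3 to a single approach, so the carry-over sentences may be headcount shorthand. This is a fair reading. However, it is contradicted by two operative sentences that name tracer only, and nothing says which governs.

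Other points, and what stands of each:

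- **It is conditional.** True: a switch must occur, in the tracer later chosen, and Aim 3 must use i.v. The PET Scans section describes only i.v. alcohol; if that governed, there would be no oral subjects. But the oral-first plan is set out in both the Statement of Purpose and section 4.1, and the switch is part of the design.
- **Oral subjects could be rescanned.** Three injections per tracer are within the cap, and the payment section provides for three scans. A baseline, an oral and an i.v. scan would fit, but no such rescan is planned.
- **The upper counts are stretched.** Five is the natural case, since the check can be made at five. Nine needs four further oral subjects. The lowest power figures also need an oral effect near zero.
- **The magnitudes are assumed.** This stands. The plan does not say that the trigger is the five-subject mean or which region it uses, and the size of the selection effect depends on that.
- **A route term would do.** Largely correct. Oral subjects exist only among controls, so a route term gives essentially the same contrast as excluding them. It is an acceptable equivalent, but it does not recover their information for the group comparison.
- **The headcount proves little.** It matches full carry-over only when Aims 1 and 2 do not overlap, and the plan hopes that they will.

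**Conclusion.** The concern holds. In the stated contingency, the rule as written places 5 to 9 oral-challenged subjects (10 at the limit) in the control group and none in the AUD group. The specified model cannot separate route from group. This is an unreconciled conflict with the single-approach commitment in the Statement of Purpose, not a declared choice to mix routes.

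The counts and the 17% to 30% shift follow from the text. The loss of power and the inflated error rate depend on the assumed effects, SD and trigger rule, and should be read as an illustration of scale. The direction is towards missing the hypothesised difference if oral has the smaller effect; selection on the first five acts the same way even if the routes are equal. It should be fixed before Aim 3 begins, so that the choice of controls is not made after the data have been seen.

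**What to change.** In section 4.1 (Aim 3) and the Breakdown of Aims 1-3, state that only Aim 1 or 2 subjects scanned with both the tracer **and the route** chosen for Aim 3 enter the Aim 3 analysis. Restate the control number as 30 minus the number of oral subjects: 25 down to 21, or 20 if all ten were oral.

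If the excluded controls are to be replaced, check the headcount. With s people shared between Aims 1 and 2 and k oral subjects replaced, (20 − s) + (20 + k) ≤ 40 requires s ≥ k. With no sharing, the moderate-drinker total becomes 45 to 49 for k = 5 to 9, and the ceiling in item 6 must rise.

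Secondary clarifications:

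- State that the Aim 1 and 2 model in item 13 is fitted separately by tracer and route, with n per route.
- Reconcile the PET Scans section (i.v. only) with section 4.1 and the Laboratory Alcohol Session section (both routes).
- Reconcile the firm switch in the Statement of Purpose with the optional one in section 4.1.

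**Cost.** Wording only. Without replacement, the Aim 3 standard error is 5% (25 v 30), 10% (21 v 30) or 12% (20 v 30) wider. There is no cost if the chosen tracer does not switch.
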